7.3.1.2. Liver Chemistry Follow-up Assessments

Chemistry tests/ assessments below are to be performed at the time of the event and then continued and/or discontinued at the discretion/judgment of the sponsor-investigator; please refer to stopping criteria within this document.

Viral hepatitis serology including:

- Hepatitis A IgM antibody;
- Hepatitis B surface antigen and Hepatitis B Core Antibody (IgM);
- Hepatitis C RNA;
- Cytomegalovirus IgM antibody;
- Epstein-Barr viral capsid antigen IgM antibody (or if unavailable, obtain heterophile antibody or monospot testing);
- Hepatitis E IgM antibody
- Serum creatine phosphokinase (CPK) and lactate dehydrogenase (LDH)
- Fractionate bilirubin, if total bilirubin >2xULN
- Obtain complete blood count with differential to assess eosinophilia
- Record the appearance or worsening clinical symptoms of hepatitis, or hypersensitivity, fatigue, decreased appetite, nausea, vomiting, abdominal pain, jaundice, fever, or rash
- Record use of concomitant medications, acetaminophen, herbal remedies, other over the counter medications, or putative hepatotoxins
- Increased alcohol use

The following assessments are required for subjects with ALT >3xULN and bilirubin >2xULN (.35% direct) but are optional for other abnormal liver chemistries:

- Anti-nuclear antibody, anti-smooth muscle antibody, and Type 1 anti-liver kidney microsomal antibodies
- Liver imaging (ultrasound, magnetic resonance, or computerized tomography) to evaluate liver disease.

Stopping Criteria:

- For subject meeting liver stopping criteria 1:
 - A repeat of liver chemistries within 24 hours, liver event follow-up assessments and close monitoring
 - A specialist or hepatology consultation is recommended
 - Monitor subjects twice weekly until liver chemistries (ALT, AST, alkaline phosphatase, bilirubin) resolve, stabilize or return to within baseline values.
- For subjects meeting criteria 2 or 3:
 - A repeat of liver chemistries within 24 to 72 hours for repeat liver chemistries and liver event follow-up assessments
 - Monitor subjects weekly until liver chemistries (ALT, AST, alkaline phosphatase, bilirubin) resolve, stabilize or return to within baseline values
- After holding ofatumumab for two weeks:
 - If the treatment is exhibiting efficacy **and** the subject wants to continue therapy after being informed of the results of liver chemistry testing, then the ofatumumab may be re-started.
 - Liver chemistries and follow-up assessments should be monitored at a minimum of every 2 weeks until resolution, stabilization, or a return to baseline values, at which point monitoring should be continued per protocol
- Subjects with $ALT > 3 \times ULN$ **but** $< 5 \times ULN$ **and** bilirubin $< 2 \times ULN$ without hepatitis symptoms or rash, and who may be monitored weekly for at least 4 weeks, then the following actions should be taken:
 - Subjects can continue ofatumumab
 - Weekly repeat of liver chemistries until they resolve, stabilize, or return to baseline values, then monitor liver chemistries as per protocol assessment schedule

If at any time the subject meets any of the liver chemistry stopping criteria, then proceed as described above.

If after 4 weeks of monitoring, $ALT < 3 \times ULN$ and $\text{bilirubin} < 2 \times ULN$ monitor twice monthly until liver chemistries normalize or return to within baseline values

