3.3 Exclusion Criteria

Subjects meeting any of the following criteria must not be enrolled in the study:

1. Subjects who have current active hepatic or biliary disease (with the exception of patients with Gilbert's syndrome, asymptomatic gallstones, liver metastases or stable chronic liver disease per investigator assessment).
2. Having received rituximab within the prior 2 months
3. Treatment with any known therapeutic or experimental therapy within 4 weeks prior to enrollment, or currently participating in any other interventional clinical study
4. Other past or current malignancy. Subjects who have been free of malignancy for at least 5 years, have a history of completely resected non-melanoma skin cancer, successfully treated in situ carcinoma, adequately treated basal or squamous cell skin cancer, adequately treated Stage I or II cancer from which the patient is currently in complete remission, or any other cancer for which the patient has been disease-free for 5 years are eligible.
5. Prior treatment with anti-CD20 monoclonal antibody or alemtuzumab within 2 months prior to start of therapy.
6. Chronic or current infectious disease requiring systemic antibiotics, antifungal, or antiviral treatment such as, but not limited to, chronic renal infection, chronic chest infection with bronchiectasis, tuberculosis and active Hepatitis C.
7. History of significant cerebrovascular disease in the past 6 months or ongoing event with active symptoms or sequelae
8. Known HIV positive
9. Clinically significant cardiac disease including unstable angina, acute myocardial infarction within six months prior to randomization, congestive heart failure (NYHA III-IV), and arrhythmia unless controlled by therapy, with the exception of extra systoles or minor conduction abnormalities.
10. Significant concurrent, uncontrolled medical condition including, but not limited to, renal, hepatic, gastrointestinal, endocrine, pulmonary, neurological, cerebral or psychiatric disease which in the opinion of the investigator may represent a risk for the patient.
11. Positive serology for Hepatitis B (HB) defined as a positive test for HBsAg. In addition, if negative for HBsAg but HBcAb positive (regardless of HBsAb status), a HB DNA test will be performed and if positive the subject will be excluded. HBsAg negative, HBsAB negative, HBsAB positive subjects can be included, * See Monitoring criteria for HBcAb+ and HBV DNA negative subjects on next page.

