 - Consult with a physician experienced in care & management of subjects with hepatitis B to manage/treat subjects who are anti-HBc positive

12. Positive serology for hepatitis C (HC) defined as a positive test for HCAb, in which case reflexively perform a HC RIBA immunoblot assay on the same sample to confirm the result
13. Pregnant or lactating women. Women of childbearing potential must have a negative pregnancy test at screening. **women of child bearing potential must undergo pregnancy testing prior to each dose if the previous pregnancy test was greater than 14 days prior and a pregnancy test at 6 months after the last dose.
14. Women of childbearing potential, including women whose last menstrual period was less than one year prior to screening, unable or unwilling to use adequate contraception from study start to one year after the last dose of protocol therapy. Adequate contraception is defined as hormonal birth control, intrauterine device, double barrier method or total abstinence.
15. Male subjects unable or unwilling to use adequate contraception methods from study start to one year after the last dose of protocol therapy.
16. Receiving warfarin

*Monitoring criteria for HBcAb+ and HBV DNA negative subjects:

- If HBV DNA is negative, subject may be included but must undergo at least every 2 month HBV DNA PCR testing from the start of treatment during the treatment course.
- Monitoring during the follow-up period will be performed during routine study visits for a minimum follow-up period of six months after the last dose, as long as the subject remains on study. Monitoring frequency during follow-up should occur at a minimum of every 2-3 months. Whenever possible, the monitoring should occur as part of the routine follow-up visit (Note: for most studies, the follow-up visits are 1 month post-dose, 3 months post-dose and 6 months post-dose).
- Prophylactic antiviral therapy may be initiated at the discretion of the investigator.

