7.0 STUDY ASSESSMENTS AND PROCEDURES

7.1 Study Calendar and Assessment Schedule

All visits should be +/- 7 business days with the exception of day 1 of cycle 1.

Procedures	≤ 14 days prior to registration[†]	Treatment				Follow-up	
		Doses 1-4 (Every week – Week 1, 2, 3, 4)	Doses 5-8 (Every week – Week 5, 6, 7, 8)	Doses 9-12 (Every 4 weeks - Week 12, 16, 20, 24)	Treatment withdrawal	1,3, 6 months following last ofatumumab dose	9, 12, 15, 18, 21, 24 months following last ofatumumab dose
Medical History	X						
Disease History	X						
Therapy History	X						
Efficacy Assessments							
¹ Bone marrow/ aspirate biopsy	X					X	
² CT/PET	X					X	X
Safety Assessments							
³ Physical Exam or Evaluation	X	³ X	³ X	³ X		X	X
³ ECOG	X	³ X	³ X	³ X		X	X
Height	X						
Weight	X					X	X
Vital Signs	X	X	X	X		X	
12-lead ECG	X						
Adverse Events		X	X	X	X	X	X
⁴ FFP (2 units)		⁴ X	X	X			
Dispense Study Medication							
Ofatumumab		X	X	X			
Lab Assessments							
⁵ Hematology	X	X	X	X		X	X
⁶ Chemistry	X	X	X	X		X	X
⁷ Liver chemistry	X	X	X	X			
⁸ Complement levels	X	X		X		X	X

Procedures	< 14 days prior to registration[†]	Treatment				Follow-up	
		Doses 1-4 (Every week – Week 1, 2, 3, 4)	Doses 5-8 (Every week – Week 5, 6, 7, 8)	Doses 9-12 (Every 4 weeks - Week 12, 16, 20, 24)	Treatment withdrawal	1,3, 6 months following last ofatumumab dose	9, 12, 15, 18, 21, 24 months following last ofatumumab dose
⁹ B-cells, IgG, IgA and IgM	X					X	
¹⁰ HIV Test	X						
¹¹ Serum Pregnancy Test	X						
Hepatitis B&C*	X						X
Survival	X					X	X

***REQUIRED- Subjects who are HBcAb positive** must undergo at least every 2 month HBV DNA PCR testing during the treatment course. Monitoring must also occur during the follow-up period for a minimum of 6 months after the last dose as long as the subject remains in the study at a minimum frequency of every 2 to 3 months.

[†] Bone marrow/aspirate biopsy and CT/PET performed within 28 days of registration.

1. BM biopsy will be performed for staging at baseline and if clinically warranted after completion of therapy. If the BM biopsy is positive at baseline it must be repeated once to confirm CR. This will include flow cytometry for minimal residual disease (MRD) status. Bone marrow (or peripheral blood if bone marrow is unavailable must be sent to the cytogenetics laboratory for analysis. If the BM biopsy is negative at baseline, it will not be repeated.

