7.3 Safety Assessments

7.3.1 Liver chemistry stopping and follow-up criteria

Liver chemistry stopping and follow-up criteria have been designed to assure subject safety and evaluate liver event etiology. The sponsor-investigator will review all events which meet liver chemistry stopping criteria to determine if the event was due to:

- tumor lysis, disease related liver involvement
- other identified cause and to exclude drug induced liver injury (DILI) due to ofatumumab

The criteria are relevant for all Ofatumumab studies because transient elevations in LFTs may be due to tumor lysis which is of clinical benefit, disease related liver involvement or due to other chemotherapy rather than drug induced liver injury from ofatumumab.

If the event is determined to be due to causes other than ofatumumab DILI and improvement is observed after withdrawal of ofatumumab, rechallenge may be attempted if deemed appropriate by the sponsor-investigator and in addition to consent of the subject.

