7.3.1.1 Liver chemistry interruption/stopping criteria

1. ALT $>3\times\text{ULN}$ **and** bilirubin $> 2 \times \text{ULN}$ ($>35\%$ direct bilirubin; bilirubin fractionation required*)
2. ALT $>8\times\text{ULN}$
3. ALT $>5\times\text{ULN}$ for more than 2 weeks

***NOTE:** If serum bilirubin fractionation not immediately available, study drug should be discontinued if ALT $> 3 \times \text{ULN}$ and bilirubin $> 2 \times \text{ULN}$. Serum bilirubin fractionation should be performed if testing is available. If testing is unavailable, record presence of detectable urinary bilirubin on dipstick, indicating direct bilirubin elevations and suggesting liver injury.

When any of the liver chemistry stopping criteria is met, do the following:

- Immediately stop study treatment
- Hold Ofatumumab for two weeks, repeat liver chemistry testing at least twice weekly, and report to sponsor-investigator to discuss the possibility of re-challenging with ofatumumab. *Note: The 2 week time point for stopping medication was chosen because it will distinguish from LFT elevations due to tumor lysis which should have resolved within this time period. Medication is interrupted and it is a clinical and patient decision if ofatumumab may be re-started. The risk: benefit ratio is different in an oncology setting and an efficacious therapy may be life-saving.*
- Report SAE to Novartis within 24 hours

- All events of ALT > 3xULN **and** bilirubin > 2xULN (>35% direct bilirubin) (or ALT>3xULN and INR>1.5, if INR measured; INR measurement is not required and the threshold value stated will not apply to subjects receiving anticoagulants), termed 'Hy's Law', **must be reported as an SAE (excluding studies of hepatic impairment or cirrhosis).**
- NOTE: if serum bilirubin fractionation is not immediately available, study treatment should be discontinued if ALT > 3xULN **and** bilirubin > 2xULN. Serum bilirubin fractionation should be performed if testing is available. If testing is unavailable, **record presence of detectable urinary bilirubin on dipstick**, indicating direct bilirubin elevations and suggesting liver injury.

Liver chemistry follow-up assessments are to be followed until liver chemistries resolve, stabilize or return to baseline values.

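### For HBcAb-positive subjects, no visible rule requires an HBV DNA result from the liver event or later before ofatumumab is restarted

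*Combined protocol and SAP*

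**What the plan says.** **HBV DNA as the control marker.** Under exclusion criterion 11 (section 3.3), a patient who is HBsAg-negative but HBcAb-positive has HBV DNA measured: "a HB DNA test will be performed and if positive the subject will be excluded". Those who enter "must undergo at least every 2 month HBV DNA PCR testing from the start of treatment during the treatment course", and the note to the section 7.1 calendar repeats the rule. Under section 7.4.6, an HBV DNA result that turns positive leads to notification of the drug supplier's clinical team. If treatment is unfinished, it also leads to a discussion with the medical monitor about continuing.

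**Liver-event work-up.** Section 7.3.1.2 lists tests to be done at the time of the event. For hepatitis B these are "Hepatitis B surface antigen and Hepatitis B Core Antibody (IgM"; for hepatitis C the same list asks for "Hepatitis C RNA". HBV DNA is not listed.

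**Hold and restart.** Section 7.3.1.1 stops treatment, holds ofatumumab for two weeks with liver chemistry at least twice weekly, and tells the site to "report to sponsor-investigator to discuss the possibility of re-challenging with ofatumumab". Section 7.3.1 adds that, for a cause other than ofatumumab-induced injury and with improvement off drug, "rechallenge may be attempted if deemed appropriate by the sponsor-investigator and in addition to consent of the subject". Section 7.3.1.2 says that after the hold, if treatment is showing efficacy and "the subject wants to continue therapy after being informed of the results of liver chemistry testing, then the ofatumumab may be re-started".

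**The concern.** At entry the protocol does not accept a negative HBsAg as enough for HBcAb-positive subjects; it asks for HBV DNA. At a liver stop, when hepatitis B reactivation is one of the explanations to rule out, the required hepatitis B tests go back to HBsAg and core IgM. No rule in the visible text brings the scheduled PCR forward, and neither restart provision asks for a current result.

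Followed as written, the rules allow restart on an HBV DNA result drawn before the event. At the minimum schedule that result could be up to about two months old; early in treatment it could be the screening result. The section 7.4.6 discussion starts only once a positive DNA result exists, so it may not be reached when the restart decision is made. What is at stake is the safety of an individual subject: re-exposure to ofatumumab during a reactivation that has not been recognised.

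**Working it through.** The plan states no figure on this point. The check is a reading of the rules, followed by a calendar calculation.

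**1. Which rules require HBV DNA?**

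| Step | Section | HBV DNA required? |
|---|---|---|
| Entry, if HBcAb-positive | 3.3 | Yes |
| On treatment | 3.3, 7.1 | Yes, at least every 2 months, by calendar |
| Work-up at a liver stop | 7.3.1.2 | No; HBsAg and core IgM |
| During the hold | 7.3.1.1 | No; liver chemistry |
| Rechallenge or restart | 7.3.1, 7.3.1.2 | No |
| After restart | 7.3.1.2 | No; the follow-up list has no HBV DNA |
| Medical-monitor discussion | 7.4.6 | Starts only from a positive result |

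So a current result at restart depends on a scheduled PCR happening to fall in the hold, or on someone choosing to order one.

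**2. How often does a scheduled PCR fall in the hold?**

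Inputs: hold H = 14 days (7.3.1.1); PCR interval T = 56 to 61 days (two months, 3.3 and 7.1). Assumptions: PCR at the minimum frequency, stop times spread evenly over the interval, restart exactly at the end of the hold.

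Share of holds with no scheduled PCR = 1 − H/T

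- T = 56: 1 − 14/56 = 0.75
- T = 61: 1 − 14/61 = 0.77

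**3. Sensitivity to the assumptions**

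- Restart at 28 days instead of 14: 1 − 28/56 = 0.50; 1 − 28/61 = 0.54.
- PCR every 30 days, more often than required: 1 − 14/30 = 0.53.
- Stops found only at visits. Assume liver chemistry on days 15 and 29 and then at the week 8, 12, 16, 20 and 24 dose visits of section 7.1. With week 1 on day 1, these are days 50, 78, 106, 134 and 162, so there are seven draw dates. Count the dates with no PCR from the stop to 14 days later:
  - PCR on days 50, 106, 162: none for stops on days 15, 29, 78, 134, which is 4 of 7.
  - PCR on days 29, 78, 134: none for stops on days 50, 106, 162, which is 3 of 7.

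Both PCR patterns keep within the two-month minimum, with no gap over 56 days. The visit-tied share therefore depends on which dates are assumed, and the protocol does not fix the PCR dates.

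**The case against.** The strongest reply is that restart is well controlled without this test. The sponsor-investigator reviews every stopping event for cause, and rechallenge after another cause needs improvement off drug, a judgment that it is appropriate, and consent. An SAE report is due within 24 hours. HBsAg is mandatory at the event, and since these subjects entered HBsAg-negative, a positive would be new information. A hepatitis B physician is to be consulted for anti-HBc-positive subjects, and antiviral prophylaxis is allowed. The two-monthly PCR is a minimum and is not suspended during a hold. The work-up list is open-ended, so HBV DNA can be added. The liver section is described as relevant to all ofatumumab studies, with HBV-specific rules placed elsewhere. Hepatitis C has no parallel PCR schedule, so the contrast with its RNA test is weak evidence.

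Most of this stands, and it is why the point is small. It does not close the gap. Each safeguard permits the test; none requires it or ties it to restart. The physician consultation is not timed to a liver event. The separate recommendation for specialist or hepatology consultation covers criterion 1 only. Reactivation could itself be classed as a cause other than drug-induced injury, so the rechallenge wording does not by itself prevent restart.

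A further limit is that Appendix 2 points by hyperlink to the prescribing information, which was not available. It may contain a relevant instruction.

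A reader might infer that restart goes ahead with no hepatitis B check, or that a subject known to be HBV DNA-positive could be restarted without further review. The documents support neither: HBsAg and core IgM are ordered at the event, and a positive DNA result before planned therapy is complete brings in the section 7.4.6 discussion.

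**Conclusion.** The gap is real and minor. For HBcAb-positive subjects, the visible rules can be met at restart without an HBV DNA result from the event or later, although HBV DNA is the marker the protocol uses for these subjects everywhere else.

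The 75-77% holds only at the minimum PCR frequency, with evenly spread stops and restart at exactly 14 days. Later restart or more frequent PCR lowers it, and the visit-tied examples give 3 of 7 or 4 of 7 depending on the dates chosen. A reader might take any of these as the chance of missing a reactivation. They are not: they describe calendar overlap only, and the documents give no frequency for reactivation, liver stops or HBcAb positivity. With approximately 12 subjects planned, few or none may be affected. No planned analysis, toxicity table or monitoring flag changes. This is a cheap safety improvement.

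**What to change.** Add to section 7.3.1.2:

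*In HBcAb-positive subjects, obtain HBV DNA PCR with the liver event follow-up assessments (at the repeat draw within 24 to 72 hours, or within 24 hours for criterion 1) when any liver stopping criterion is met. The result must be available before ofatumumab is restarted. If it is positive, follow section 7.4.6.*

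The sample is tied to the repeat draw because a stop is known only once the triggering result is back. The stopping thresholds, the two-week hold and the other tests stay as they are.

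The cost is one sentence of wording and one extra assay per affected subject, already used in the trial and taken at a draw the protocol already requires. The downside is a possible short delay to restart if the result takes longer than the hold.

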7.4. Adverse Events

The investigator or site staff will be responsible for detecting, documenting and reporting events that meet the definition of an AE or SAE.

7.4.1 Definition of an AE

Any untoward medical occurrence in a subject or clinical investigation subject, temporally associated with the use of a medicinal product, whether or not considered related to the medicinal product.

Events meeting the definition of an AE include:

- Any abnormal laboratory test results (hematology, clinical chemistry, or urinalysis) or other safety assessments e.g., ECGs, radiological scans, vital signs measurements), including those that worsen from baseline, and felt to be clinically significant in the medical and scientific judgment of the investigator
- Exacerbation of a chronic or intermittent pre-existing condition including either an increase in frequency and/or intensity of the condition
- New conditions detected or diagnosed after study product administration even though it may have been present prior to the start of the study
- Signs, symptoms, or the clinical sequelae of a suspected interaction
- Signs, symptoms, or the clinical sequelae of a suspected overdose of either study product or a concomitant medication (overdose per se will not be reported as an AE/SAE)

“Lack of efficacy” or “failure of expected pharmacological action” per se will not be reported as an AE or SAE. However, the signs and symptoms and/or clinical sequelae resulting from lack of efficacy will be reported if they fulfill the definition of an AE or SAE.

Events that **do not** meet the definition of an AE include:

- Any clinically significant abnormal laboratory finding or other abnormal safety assessments that is associated with the underlying disease, unless judged by the investigator to be more severe than expected for the subject’s condition.
- The disease/disorder being studied, or expected progression, signs, or symptoms of the disease/disorder being studied, unless more severe than expected for the subject’s condition
- Medical or surgical procedure (e.g., endoscopy, appendectomy); the condition that leads to the procedure is an AE
- Situations where an untoward medical occurrence did not occur (social and/or convenience admission to a hospital)
- Anticipated day-to-day fluctuations of pre-existing disease(s) or condition(s) present or detected at the start of the study that do not worsen
- B cell depletion and hypogammaglobulinemia due to ofatumumab treatment

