Interim analysis for the pivotal trial evaluated 154 patients with refractory CLL (Study Hx-CD20-406). In the 138 evaluable patients, approximately half were refractory to both fludarabine and alemtuzumab and the other patients were refractory to fludarabine and considered inappropriate for alemtuzumab due to bulky disease of the lymph nodes. An objective response rate of approximately 50% consisting of 30 partial responses was achieved in the fludarabine and alemtuzumab refractory group and an objective response rate of approximately 44% was achieved in the fludarabine refractory group including 1 complete response and 34 partial responses. In this study, ofatumumab was generally well tolerated by the patients. The most frequently reported adverse events (>15% frequency) were pyrexia, diarrhea, fatigue, cough, neutropenia, anemia and pneumonia. There were no unexpected safety findings. Studies clearly indicate monoclonal antibodies (mAbs) play an important role in the treatment of CLL. Anti-CD20 mAbs with a low toxicity can be applied advantageously in subjects who cannot tolerate highly toxic treatments (i.e. advanced age), in combination with chemotherapy and as maintenance treatment. Ofatumumab preclinical data demonstrates superior CDC activity in CLL compared to rituximab. Based on this, therapeutic combinations that may exploit the enhanced CDC potential would be hypothesized to improve outcome.

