7.4.3 Toxicity Assessments of AEs and SAEs

The investigator is required to make an assessment of the toxicity grade of each AE or SAE reported. In this protocol, the maximum toxicity grade of each non-hematologic AE/SAEs will be evaluated according to the National Cancer Institute (NCI) Common Toxicity Criteria for Adverse Events (CTCAE) version 4.0.

It is important to consider low blood counts at the initiation of therapy when evaluating hematologic toxicity of CLL subjects.

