7.4.4 Laboratory and Other Safety Assessment Abnormalities Reported as AEs and SAEs

- Any abnormal laboratory test results (hematology, clinical chemistry, or urinalysis) or other safety assessments (e.g., ECGs, radiological scans, vital signs measurements), including those that worsen from baseline, and felt to be clinically significant in the medical and scientific judgment of the investigator **are** to be recorded as AEs or SAEs.
- All events meeting liver stopping criteria must be recorded as an SAE.
- However, any clinically significant safety assessments that are associated with the underlying disease, unless judged by the investigator to be more severe than expected for the subject's condition, are **not** to be reported as AEs or SAEs.
- B cell depletion, IgG below LLN, low CD19+ count, and hypogammaglobulinemia due to treatment with ofatumumab are **not** to be reported as AEs or SAEs.

- Infusion related AEs may lead to a prolonged infusion time. Overnight stay at the hospital due to slow infusion rate is **not** to be reported as a SAE.

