8.4 Safety Evaluation

Data from all subjects who receive any study drug will be included in the safety analyses. The severity of the toxicities will be graded according to the NCI CTCAE v4.0 whenever possible. Unacceptable toxicity (> grade 3) experienced in patients will be monitored according to guidelines for monitoring toxicity in pilot/phase II trials using sequential probability ratio test based criteria. The guidelines will be used to raise a flag if the number of patients who experience unacceptable toxicity is greater than 20%. Toxicity information recorded will include the type, severity, date of onset, date of resolution, and the probable association with the study regimen. Tables will be constructed to summarize the observed incidence by severity and type of toxicity. Baseline information (e.g. the extent of prior therapy, extent of disease) and demographic information will be presented, as well, to describe the patients treated in this Phase II study.

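### Cytopenias put down to CLL are left out of adverse event recording unless judged worse than expected, with no objective criterion, so hematologic toxicity can be under-counted

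*Combined protocol and SAP*

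**What the plan says.** **Definition and exclusion.** Section 7.4.1 defines an AE "whether or not considered related to the medicinal product". It counts abnormal hematology results as AEs, "including those that worsen from baseline, and felt to be clinically significant in the medical and scientific judgment of the investigator". Its list of occurrences that are not AEs then includes "Any clinically significant abnormal laboratory finding or other abnormal safety assessments that is associated with the underlying disease". The one exception is a finding that the investigator considers worse than the subject's disease would lead one to expect. Section 7.4.4 states the inclusion rule and follows it with the same exclusion and exception for AEs and SAEs: "any clinically significant safety assessments that are associated with the underlying disease".

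**Grading.** In Section 7.4.3, "the maximum toxicity grade of each non-hematologic AE/SAEs will be evaluated according to" CTCAE v4.0. For hematologic toxicity that section only asks assessors to bear low starting counts in mind. Section 8.4 grades toxicities by CTCAE v4.0 where possible and does not set hematologic events apart.

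**Use.** Toxicity is a secondary objective (Section 1.0). Sections 8.1 and 8.4 tabulate it by severity and type. Section 8.4 also applies a flag, based on a sequential probability ratio test (SPRT), when more than 20% of patients have toxicity above grade 3.

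**Data available.** Section 7.1, footnote 5, schedules hematology before treatment, every two weeks in the first month, then monthly to at least six months after the last dose. Section 8.3 summarizes hematology values by mean (s.d.) or median (range).

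**The concern.** The AE definition is free of causality, but the laboratory exclusion brings causality back before the event is recorded. Section 8.4 plans to record the probable association of each toxicity with the regimen, which treats attribution as something to report. For disease-associated laboratory findings, attribution decides instead whether there is anything to report.

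Relapsed CLL itself lowers blood counts, the investigator knows the treatment, and no control arm shows what the disease alone would do. The protocol's own account of the pivotal ofatumumab trial says: "The most frequently reported adverse events (>15% frequency) were pyrexia, diarrhea, fatigue, cough, neutropenia, anemia and pneumonia". Two of those seven events are cytopenias, so the exclusion falls on toxicity that is expected with this drug. If some of it is misattributed, reported incidence is biased downward and the flag sees fewer events than occurred.

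**Working it through.** **Step 1: can a worsened count still be excluded?** The inclusion rule needs clinical significance in the investigator's judgment. The exclusion acts on findings that are already clinically significant, and Section 7.4.4 places it after the inclusion rule as a qualification. A worsened, clinically significant count can therefore meet the inclusion rule and still be excluded. That takes two judgments: that the finding is associated with CLL, and that it is no more severe than expected. The documents attach no grade, threshold or change from baseline to the second.

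**Step 2: which counts are exposed?** Section 3.2 requires hemoglobin of at least 9.0 g/dl and platelets of at least 50,000/mm³, and sets no neutrophil minimum. Severe anemia or thrombocytopenia on study would be a visible fall from an entry value. Severe neutropenia could already be present at entry, so it is the easiest to call expected.

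**Step 3: does anything downstream recover the events?** No section grades the measured counts independently of AE reporting. A mean or median does not give the number of patients who reached a grade.

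**Step 4: the plan's own figure.** The 20% flag cannot be reproduced. Section 8.4 gives no null or alternative rate, error rates or boundaries for the SPRT.

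**Step 5: illustration.** This is one look at full accrual, not the SPRT.

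- Number of patients n: 12 (study synopsis and Section 3.1) or 36 (Section 8.2). The documents give both.
- Smallest count k with k/n above 0.20: 0.20 × 12 = 2.4, so k = 3; 0.20 × 36 = 7.2, so k = 8.
- True rate of toxicity above grade 3: 35% (assumed).
- Loss d: 5 points (assumed) or 6 points. Six borrows the phase I rate of grade 3–4 neutropenia in Section 2.3, as if all of it were above grade 3 and unrecorded.
- Formula: P(X ≥ k), with X binomial (n, 0.35 − d).

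For n = 12 at 0.35: 1 − (0.0057 + 0.0368 + 0.1088) = 0.849. At 0.29: 1 − (0.0164 + 0.0804 + 0.1807) = 0.722.

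| Recorded rate | n = 12, 3 or more | n = 36, 8 or more |
|---|---|---|
| 35% (nothing lost) | 0.849 | 0.967 |
| 30% (5 points lost) | 0.747 | 0.888 |
| 29% (6 points lost) | 0.722 | 0.861 |

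**Step 6: sensitivity.** Suppose instead that a quarter of affected patients go unrecorded. With a true rate of 30%, the chance falls from 0.747 to 0.528 (n = 12) or from 0.888 to 0.581 (n = 36). With a true rate of 40%, it falls from 0.917 to 0.747 or from 0.993 to 0.888. The direction is the same throughout; the size follows the assumptions.

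**The case against.** A reader might infer that cytopenias ascribed to CLL are never recorded as AEs. The documents do not support that. The exclusion carries its exception in the same sentence, and hematology results that worsen from baseline are expressly named as AEs when clinically significant. Exacerbation of a pre-existing condition also counts, and Section 7.4.2 gives blood dyscrasias among its examples of serious events. A cytopenia that the investigator attributes to treatment is not excluded. Loss arises only through misattribution, which is possible but not automatic.

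A reader might also infer that the flag is badly disabled. If 15 of the assumed 35 points were lost, the chance of exceeding 20% would fall to 0.44 (n = 12) or 0.43 (n = 36). That arithmetic is right, but 15 points is not a figure from the documents. The only cytopenia severity rate they give is 6% grade 3–4 neutropenia, and this includes grade 3, which the flag as written does not count. Anemia and thrombocytopenia could add to it, but no severity rate is given for them. The list of events above 15% in Section 2.3 is not split by grade and cannot fill the gap.

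Finally, the counts are not lost as data, and some allowance for low starting counts is deliberate (Section 7.4.3). A shift table could be made later even if unplanned. This limits the seriousness. It does not remove the point: the plan as written does not call for such a table, and the toxicity tables and flag would rest on the filtered record.

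**Conclusion.** The point holds in limited form. Whether a disease-associated cytopenia is recorded depends on attribution and on a severity judgment with no objective criterion, and no planned analysis grades the counts independently. In an uncontrolled trial this can bias hematologic toxicity downward. Events of any grade can be missing from the toxicity tables; only those above grade 3 can be missing from the flag.

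The size cannot be derived from the documents. The drop from 0.85 to 0.75–0.72 with 12 patients, or from 0.97 to 0.86 with 36, rests on an assumed 35% true rate, an assumed loss of 5 to 6 points (6 points for n = 36), and one look at full accrual in place of the unspecified SPRT. The 6-point figure also comes from a phase I trial with four weekly doses of ofatumumab, not twelve doses with plasma. This is a cheap improvement worth making; it does not show that the safety monitoring fails.

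**What to change.** In Section 8.4:

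1. For all treated patients, tabulate worst post-baseline against baseline grade for neutrophils, platelets and hemoglobin, derived from the scheduled counts whatever the AE attribution.
2. Name one grading scale for these counts. First reconcile Section 7.4.3, which names CTCAE v4.0 for non-hematologic events only, with Section 8.4, which applies it to toxicities generally.
3. Report attribution to CLL or to the regimen as a column.
4. Show the toxicity-flag count with and without laboratory-derived new worsening to above grade 3.

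The AE and SAE reporting rules need not change for this. The cost is SAP wording and one table from data already collected. The downside is that reported hematologic toxicity will look higher and part of it is disease; the baseline grade makes that part visible, and the two flag counts keep the effect open to inspection.
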